8.3.3 Expected Adverse Events

An adverse event (AE) is considered "expected" if:

- For approved and marketed drugs or devices, those adverse events are described in the approved Package Insert (Label).
- For investigational new drugs or devices, those adverse events are described in the FDA Investigator's Brochure.
- In clinical research studies, information on expected adverse events is also summarized in the protocol and in the consent document. See section 9.1 for the list of expected adverse events related to the drug under study.

8.3.4 Unexpected Adverse Event

An adverse event (AE) is considered "unexpected" if it is not described in the Package Insert, Investigator's Brochure, in published medical literature, in the protocol, or in the informed consent document.

8.4 Adverse Event Characteristics

8.4.1 CTCAE Term

(AE description) and grade: The descriptions and grading scales found in the NCI Common Terminology Criteria for Adverse Events (CTCAE) version 4.0 will be utilized for AE reporting. All appropriate treatment areas should have access to a copy of the CTCAE version 4.0. A copy of the CTCAE version 4.0 can be down loaded from the CTEP web site. (http://ctep.cancer.gov)

8.4.2 Attribution of the AE

The investigator or co-investigator is responsible for assignment of attribution.

Definite – The AE *is clearly related* to the study treatment.

Probable – The AE is likely related to the study treatment.

Possible – The AE may be related to the study treatment.

Unlikely – The AE is doubtfully related to the study treatment.

Unrelated – The AE is clearly NOT related to the study treatment.

8.5 Serious Adverse Event Reporting Guidelines

The Sponsor Investigator will report SAEs to regulatory bodies and to the participating sites in the following manner:

Sponsor SAE Reporting

Event occurring	Repo	ort to:	Event occurring	Report to:		
30 Days post last itacitinib dose	FDA / IRB/Incyte	Consortium	post last itacitinib dose	FDA / IRB/ Incyte	Consortium	
All SAEs; ✓ Expected or Unexpected ✓ Possible, Probable, or Definite	24 hours from knowledge	Monthly	 SAEs – ✓ Expected ✓ Probable or Definite OR ✓ Unexpected ✓ Possible, Probable or Definite 	24 hours from knowledge	Monthly	

- 8.5.2 The Principal Investigator must be notified within 3 business day of study team's knowledge of any event meeting the criteria and definition of a serious adverse event, regardless of attribution, occurring during the study or within 30 days of the last administration of the itacitinib. Incyte should be notified by the PI within 24 hours to enable reporting to regulatory authorities as required.
- 8.5.3 The investigator must report all events meeting the criteria and definition of a serious adverse event that are unexpected and possibly related (definite, probable or possible to study treatment administration) to the local IRB as per local IRB policy.
- 8.5.4 All Serious Adverse Events will be reported using the Serious Adverse Event form within 3 days of first awareness of the event to the MAGIC Data Coordinating Center. A copy of the form should be sent to the MAGIC Coordinator via email to **[contact]**.

The MAGIC Data Coordinating Center will disseminate information regarding serious adverse events to the participating sites within 3 days of review of the information by [name] if the event(s) is believed to be related (i.e. probably or definitely) to the study medication. All other Serious Adverse Events will be discussed on monthly webinars held with all participating centers (see section 12).

The Principal Investigator will be responsible for reporting of events to the FDA and supporters, as appropriate and defined in the regulations under 21 CFR 312.32.

8.5.5 SAE/Pregnancy Reporting to Incyte:

Initial Serious Adverse Events (SAEs) and/or subsequent follow-up reports will be reported to Incyte via email to: [contact], fax (+) [name]. SAE reports should be for a single subject with any additional documents (i.e. discharge summary, relevant test results) included for the same subject as individual attachments to the email. One email can have multiple attachments as

long as each attachment contains relevant information for the same subject.

Please email your SAE form with a cover sheet and any additional attachments to the IST email address: [contact], fax (+) [name]

Reporting pregnancies to Incyte

An "Initial Pregnancy Report" or equivalent must be completed in full and emailed to [contact], fax (+) [name] within 24 hrs of discovery of a pregnancy of a subject who has taken itacitinib or the pregnancy of a partner for a subject who has taken itacitinib. The "Follow-up Pregnancy Report Form" or equivalent must be completed and emailed to [contact], fax (+) [name] within 30 days after delivery, so that Incyte is provided with information regarding the outcome of the pregnancy. If the pregnancy results in any events which meet the serious criteria (i.e., miscarriage or termination), the SAE reporting process needs to be followed and the timelines associated with an SAE should be followed

8.6 Reporting of Unanticipated Problems

Upon becoming aware of any incident, experience, or outcome (not related to an adverse event) that may represent an unanticipated problem involving risks to subjects or others, the investigator should assess whether the incident, experience, or outcome represents an unanticipated problem. The incident, experience or outcomes are considered unanticipated if it meets all of the following criteria:

- 1. Unexpected (not previously documented in terms of nature, severity, or frequency);
- 2. Causally related or possibly related to participation in the study; and
- 3. Suggests that the research places subjects or others at a greater risk of harm than was previously known or recognized.

If the investigator determines that the incident, experience, or outcome represents an unanticipated problem, the investigator must report it to the MAGIC Data Coordinating Center within 3 days of first awareness of the events, and to the local IRB as per local IRB policy.

8.7 Stopping Rules

We will monitor the study subjects for both efficacy and toxicity. We will allow continuous accrual on to the study unless a stopping rule is met or the target accrual is reached. The study may also be stopped based on the recommendation of the investigators, the TCI DSMC, or at Incyte's discretion for any reason.

Steroid-refractory GVHD:

We expect itacitinib monotherapy to be safe because of its extensive use in >700 patients prior to this trial. However, in order to protect study subjects we have designed three stopping rules that will terminate the trial early if itacitinib monotherapy as a treatment for GVHD is either too toxic or ineffective. First, our preliminary data show that the incidence of steroid-refractory GVHD using the definition in section 2.3 in the low risk population eligible for this trial is 38%. For an itacitinib monotherapy trial to be successful, the proportion of patients who develop steroid-refractory GVHD should not exceed 38%. We expect that patients who do not respond to itacitinib will be responsive to steroid treatment and we will continuously monitor the incidence of steroid-refractory GVHD in all study subjects. Patients will be considered to have steroid refractory GVHD if their GVHD is treated with systemic steroids and they either do not respond by day 28 of steroid treatment. The trial will be halted if the incidence of steroid-refractory GVHD is greater than the

associated boundary value b_k listed in the table below, among the k patients enrolled in the trial, then accrual will be halted.

Maximum # of Patients, k	5	6-8	9-10	11-13	14-16	17-19	20-22	23-25	26-28	29-31	32-35
Boundary, b _k	3	4	5	6	7	8	9	10	11	12	13
Maximum # of Patients, k	36-38	39-41	42-44	45-48	49-51	52-54	55-58	59-61	62-65	66-68	69-70
Boundary, b _k	14	15	16	17	18	19	20	21	22	23	24

Specifically, if more than 3 out of the first 5 patients, 4 out of the first 8 patients, 5 out of the first 10 patients, 6 out of the first 13 patients, or 24 out of the first 70 patients, experience steroid-refractory GVHD, the trial will be halted for safety considerations.

The operating characteristics of this stopping rule are as follows:

	True Steroid Refractory Rate 24% 30% 33% 0.38 40% 42%						
Probability of Early Stopping	0.10	0.36	0.54	0.83	0.88	0.94	

Using these boundaries, if the true steroid refractory rate is 24%, 30%, 33%, 38%, 40% or 42%, the probability of stopping the trial early is 0.10, 0.36, 0.54, 0.83, 0.88, and 0.94 respectively.

Serious infections:

Itacitinib monotherapy has been shown to be safe in over 700 patients. However, its use as a therapy for acute GVHD is investigational. The primary toxicity of treatment for GVHD is infection. Our preliminary data show that the incidence of serious infections in the first 90 days of systemic steroid treatment for GVHD is 59%. Therefore, if the proportion of study patients who experience serious infections exceeds 59%, we would not further study itacitinib monotherapy for GVHD treatment. If the incidence of serious infections is greater than the associated boundary value bk listed in the table below among the k patients enrolled in the trial, then accrual will be ended.

Maximum # of Patients, k	6	7	8-9	10-11	12-14	15-16	17-18	19-20	21-22	23-24
Boundary, b _k	4	5	6	7	8	9	10	11	12	13
Maximum # of Patients, k	25-27	28-29	30-31	32-34	35-36	37-38	39-41	42-43	44-45	46-48
Boundary, b _k	14	15	16	17	18	19	20	21	22	23
Maximum # of Patients, k	49-50	51-52	53-55	56-57	58-60	61-62	63-65	66-67	68-70	
Boundary, b _k	24	25	26	27	28	29	30	31	32	

Specifically, if more than 4 out of the first 6 patients, 5 out of the first 9 patients, 10 out of the first 20 patients, 14 out of the first 31 patients, or 29 out of the first 70 patients, experience serious infections within 3 months, the trial will be halted for safety considerations.

The operating characteristics of this stopping rule are as follows:

	True Serious Infections Rate 35% 41% 45% 50% 55% 60%					
Probability of Early Stopping	0.10 0.31 0.55 0.79 0.96 0					

Using these boundaries, if the true serious infections rate is 30%, 33%, 40%, 45%, 50% or 60%, the probability of stopping the trial early is 0.10, 0.18, 0.57, 0.83, 0.96, and 1 respectively.

Non-relapse mortality:

In this low risk patient population the the six-month non-relapse mortality rate is 9%. If, in the unlikely event that itacitinib-related toxicities increased the risk for non-relapse mortality we would want to terminate the trial early. We will continuously monitor the rate of non-relapse mortality. The trial will be halted if there is sufficient evidence that the six month NRM rate is higher than 9%. Specifically, if the incidence of non-relapse deaths within 6 months of study administration is greater than the associated boundary value b_k listed in the table below, among the k patients enrolled in the trial, then accrual will be halted for safety considerations.

Maximum # of Patients, k	11	12-26	27-45	46-65	66-70
Boundary, b _k	1	2	3	4	5

Specifically, if more than 1 out of the first 11 patients, 2 out of the first 26 patients, 3 out of the first 45 patients, 4 out of the first 65 patients, or 5 out of the first 70 patients, experience NRM within 6 months of study administration, the trial will be halted for safety considerations.

The operating characteristics of this stopping rule are as follows:

	True NRM Rate					
	3%	6%	8%	9%	11%	
Probability of Early Stopping	0.10	0.45	0.68	0.77	0.89	

Using these boundaries, if the true NRM rate is 3%, 6%, 8%, 9%, or 11%, the probability of stopping the trial early is 0.10, 0.45, 0.68, 0.77, and 0.89 respectively.

All the stopping rules were computed using the toxbdry function in R and calculations of this function are based on methods described in Chapter 12 of Jennison and Turnbull and in the illustrative paper by Ivanova, Qaquish and Schell^{46,47}.

An enrollment rule to prevent an excessive number of toxicities as described in Song and Ivanova will be used to inform us of the number of additional patients we can recruit when the current patient has not yet completed follow-up⁴⁸ Formally, the trial can enroll *m* new patients such that $r + x + m \le b_{n+m} + M$, $r + x + m - 1 < b_{n+m-1} + M$, and $n + m \le K$ where *r* is defined as the number of patients that have not completed follow-up and are still being followed for toxicity; *x* is the number of patients that have experienced toxicity, *n* is the total number of patients enrolled to date and *M* is the fixed design parameter. To be able to complete this low-risk study in a timely manner, we allow *M* to be 30.

All the stopping rules were computed using the toxbdry function in R and calculations of this function are based on methods described in Chapter 12 of Jennison and Turnbull and in the illustrative paper by Ivanova, Qaquish and Schell^{46,47}.

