2.3 Primary Endpoint

Proportion of patients who achieve CR or PR by day 28 of treatment with itacitinib without the addition of any other systemic GVHD treatment including steroids.

CR is defined as absence of GVHD symptoms. PR is defined as improvement in one or more organs involved with GVHD symptoms without progression in other organs. For a response to be scored as CR or PR on day 28, the patient must be in CR or PR on day 28 and have had no intervening systemic therapy for acute GVHD other than itacitinib.

Secondary endpoints:

- Cumulative incidence of steroid-refractory GVHD (defined as GVHD that worsens (increase by one or more grade) after 3 days, or fails to respond to treatment within 7 days (for GVHD grade III) or 14 days (for GVHD grade II) or 2nd line therapy beyond systemic steroid treatment is begun within 28 days of starting steroids.
- 2. Distribution of maximal GVHD grade (I-IV) by day 28 after starting treatment with itacitinib
- 3. Cumulative incidence of serious infections (defined as bacteremia, CMV infection needing treatment, EBV infection needing treatment, or invasive fungal infection)
- 4. Overall survival at 6 and 12 months
- 5. Cumulative incidence of NRM at 6 and 12 months
- 6. Relapse rate at 6 and 12 months
- 7. Cumulative incidence of chronic GVHD requiring systemic steroid treatment by one year from enrollment

8. Cumulative steroid dose (over 4 weeks) in patients who receive steroids as second line therapy

Safety endpoints

1. Number and proportion of patients developing reportable AEs and SAEs according to relatedness to study drug and stratified by severity

Exploratory endpoints

1. GVHD biomarker concentrations (ST2 and REG3) and their associations with clinical endpoints at day 28 after starting treatment with itacitinib

The two hypotheses are: 1) that GVHD biomarkers will remain low in study patients who respond to itacitinib treatment, but will rise in non-responders and (2) biomarker concentrations will be equivalent to those in historical control patients who respond to steroid treatment for low risk GVHD.

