7.1.3 Steroid refractory GVHD

The first salvage therapy for patients who are not responding to itacitinib is systemic steroid treatment. Patients treated with systemic steroids whose GVHD worsens (increase by one or more grade) after 3 days, **or** fails to respond to treatment within 7 days (for GVHD grade III) **or** 14 days (for GVHD grade II) **or** who start additional lines of therapy beyond systemic steroid treatment within 28 days of starting steroids will be considered steroid refractory. Escalation of steroid doses during treatment for GVHD are not considered in the definition of steroid refractory GVHD.

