7.1.5 Lines of GVHD therapy

The initiation of systemic steroids for treatment of GVHD will be considered second line therapy. Any additional systemic immunosuppression treatment to steroid therapy for acute GVHD will be considered 3rd line therapy and considered a failure to respond to steroid treatment. Resumption or changes in GVHD prophylaxis (e.g., substitution of mycophenolate for tacrolimus due to PRES) are not considered new lines of therapy. Topical steroids and non-absorbable oral steroids are not considered new lines of therapy.

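### The steroid-refractory stopping rule in section 8.7 takes its 38% benchmark from one definition and its event count from another, so it may not have its stated stopping probability

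*Combined protocol and SAP*

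**What the plan says.** Section 8.7 gives the source of its benchmark: "the incidence of steroid-refractory GVHD using the definition in section 2.3 in the low risk population eligible for this trial is 38" per cent. It adds that "we will continuously monitor the incidence of steroid-refractory GVHD in all study subjects", so the denominator is everyone enrolled. It then defines the event to be counted as a patient whose GVHD is "treated with systemic steroids and they either do not respond by day 28 of steroid treatment". The word *either* is never completed.

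Section 2.3 (secondary endpoint 1) is different. Steroid-refractory GVHD is "defined as GVHD that worsens (increase by one or more grade) after 3 days, or fails to respond to treatment within 7 days" for grade III or 14 days for grade II, or a case where "2nd line therapy beyond systemic steroid treatment is begun within 28 days of starting steroids". Section 7.1.3 has the same limbs and says that patients "who start additional lines of therapy beyond systemic steroid treatment within 28 days of starting steroids will be considered steroid refractory". It also states: "Escalation of steroid doses during treatment for GVHD are not considered in the definition of steroid refractory GVHD". Section 11.1 refers back to section 2.3 for this outcome.

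Two further passages matter. Section 7.1.5 says that systemic immunosuppression added to steroids is "considered 3rd line therapy and considered a failure to respond to steroid treatment". Section 11.2 gives the historical steroid-refractory rate as 33%, where the synopsis and section 8.7 give 38%.

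**The concern.** A stopping rule compares a running count with boundaries chosen around a benchmark rate. The comparison means what it says only if the count and the benchmark use the same event. Here the benchmark rests on limbs that can be met well before steroid day 28, and the counting sentence omits them.

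The rule carries weight in this design. The synopsis and section 11.2 accept a 15-point lower response rate only on condition that steroid-refractory GVHD does not increase, and section 11.2 also uses this outcome in the decision about a phase III trial. If the monitored event is looser or later than the benchmark event, the safeguard behind that condition is weaker than its operating characteristics suggest. The rate reported for secondary endpoint 1 would also differ from the count used to monitor the trial.

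**Working it through.** **Step 1. Who is classified differently.** Reading the sections side by side, after systemic steroids start:

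| Course on steroids | 2.3 / 7.1.3 | 8.7 as printed |
|---|---|---|
| Worsens by a grade after day 3, then responds by day 28 on steroids alone | Refractory | Not counted |
| Grade III unresponsive at day 7, or grade II at day 14, then responds by day 28 on steroids alone | Refractory | Not counted |
| Further systemic agent added within 28 days | Refractory | Counted, when read with 7.1.5 |
| Grade I, no worsening, unresponsive at day 28, no agent added | Not refractory (no response deadline for grade I) | Counted |

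The first two rows still hold if the steroid dose was raised, because 7.1.3 ignores escalation. Section 2.3 has no response deadline for grade IV either.

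**Step 2. Reproduce the printed operating characteristics.** Inputs are the 8.7 boundaries b_k for k = 5 to 70, from b_5 = 3 to b_70 = 24. With event probability p and X_k events among k patients:

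P(X_k = x) = (1 − p)·P(X_{k−1} = x) + p·P(X_{k−1} = x − 1)

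At each k from 5 to 70, the probability at x > b_k is moved to *stopped*, and the stopped amounts are added up.

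| True rate | 24% | 30% | 33% | 38% | 40% | 42% |
|---|---|---|---|---|---|---|
| Printed | 0.10 | 0.36 | 0.54 | 0.83 | 0.88 | 0.94 |
| Recomputed | 0.100 | 0.361 | 0.548 | 0.819 | 0.890 | 0.939 |

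All six agree to about 0.01. Stopping at x ≥ b_k instead gives 0.241 to 0.972 and does not match. The table is therefore correct for whatever rate is actually counted.

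**Step 3. Sensitivity to an undercount.** Let u be the net share of section 2.3 cases that 8.7 does not count. The documents do not give u, so it is an assumption. The counted rate is 0.38 × (1 − u).

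| Assumed u | Counted rate | P(stop) | Expected enrolment |
|---|---|---|---|
| 0 | 0.380 | 0.82 | 35 |
| 5% | 0.361 | 0.73 | 40 |
| 10% | 0.342 | 0.62 | 45 |
| 13% | 0.331 | 0.55 | 48 |
| 20% | 0.304 | 0.39 | 55 |
| 30% | 0.266 | 0.19 | 62 |

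If the day-28 wording instead added cases on balance, so that a true 38% was counted as 40%, the probability would rise to 0.89.

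**Step 4. Timing.** A case that rests on an early limb and is still unresponsive at day 28, with no added agent, is counted under both definitions but later under 8.7. The delay is 28 − 14 = 14 days (grade II), 28 − 7 = 21 days (grade III), or up to 28 − 3 = 25 days (worsening). At the planned 4 patients a month, taking 30 days to a month, 4 × 14/30 = 1.9 and 4 × 25/30 = 3.3. Roughly 2 to 3 more patients would enrol in that interval.

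**The case against.** The strongest reply is that this is a drafting slip and not a second definition. The sentence is visibly unfinished, its own paragraph cites section 2.3 for the benchmark, and 7.1.3 and 11.1 point the same way. That is probably the intent, but the lost words cannot be recovered. If the missing limb was added therapy, the early limbs would still be absent. An incomplete event definition inside a stopping rule needs correcting on either account.

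Three stronger readings are tempting, and the documents do not support them.

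- *Patients rescued by a further agent drop out of the count.* They do not: section 7.1.5 makes added systemic therapy a failure to respond to steroids. What can be missed is early failure followed by response on steroids alone.
- *The rule is necessarily more permissive.* The direction is likely but unproven, because 2.3 has no response deadline for grade I or IV and a day-28 limb can add such cases.
- *The plan's own figures show a fall from 0.83 to 0.54.* This treats the gap between 38% and 33% (1 − 67% day-28 response) as the effect of the definition. No section says so. The 67% describes first-line steroid treatment, and section 11.2 calls 33% the historical refractory rate itself, so the gap may be two inconsistent versions of one benchmark.

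The delay is also modest beside an enrolment rule that already allows for incomplete follow-up with M = 30, and the monitoring committee may recommend stopping at any time.

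**Conclusion.** The concern holds as a mismatch of definitions within section 8.7. Followed as written, the rule compares a count on one definition with a benchmark on another, and it declares some events 14 to 25 days later. Its stopping probability at a true 38% section 2.3 rate may then differ from the stated 0.83.

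The size is conditional. Net undercounts of 5% to 20% would give about 0.73 to 0.39, against 0.82 with none. These figures assume independent patients, a check after every patient from the fifth, outcomes known at each check, and an undercount that the documents do not report. They illustrate how steep the rule is in the counted rate and do not demonstrate a loss. The printed table itself is not in error.

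**What to change.** In section 8.7, replace the day-28 sentence with a statement that an event is counted on the date the patient first meets the definition in 2.3/7.1.3. This is the definition the 38% already rests on, so the boundaries and the printed operating characteristics can stay. Report non-response at steroid day 28 separately as a descriptive result.

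Reconcile the 38% historical rate in the synopsis and 8.7 with the 33% in section 11.2, and state the definition and patient group behind the figure that is kept.

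The cost is a short amendment. The GVHD staging and treatment records needed are already in the Time and Events Table. The downside is that slightly more or fewer events may be counted than under the day-28 wording. In particular, grade I non-response at day 28 without an added agent would appear only in the descriptive result.

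### Section 8.7 gives two conflicting serious-infection stopping boundaries and two conflicting sets of stopping probabilities (0.55 against 0.83 at a true rate of 45%)

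*Combined protocol and SAP*

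**What the plan says.** All of this is in section 8.7, under serious infections.

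- The rule is tied to the table: "If the incidence of serious infections is greater than the associated boundary value bk listed in the table below among the k patients" enrolled, accrual ends. The table covers 6 to 70 patients.
- A sentence then restates it. The trial halts at more than 4 of 6, "5 out of the first 9 patients, 10 out of the first 20 patients, 14 out of the first 31 patients". The last cut-off in that sentence, which applies at full accrual, is "29 out of the first 70 patients, experience serious infections within 3 months, the trial will be halted for safety considerations".
- An operating-characteristics table is headed "True Serious Infections Rate 35% 41% 45% 50% 55% 60" (per cent). Its readable probabilities are 0.10, 0.31, 0.55, 0.79 and 0.96 for 35% to 55%. The 60% entry is damaged in the text and is not used here.
- The next sentence claims to use the same boundaries but has other rates and values: "if the true serious infections rate is 30%, 33%, 40%, 45%, 50% or 60" per cent, "the probability of stopping the trial early is 0.10, 0.18, 0.57, 0.83, 0.96, and 1 respectively".

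The historical rate that the rule guards against is 59% in the first 90 days of steroid treatment.

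**The concern.** The rule is applied continuously and ends accrual, so for any count of infections among k patients it must give one answer. Here the table and the sentence that restates it give opposite answers at several counts, both in binding language, and no order of precedence is stated. A monitoring committee looking at 11 infections in 20 patients would have to choose between them after seeing the data, which defeats the purpose of a prespecified rule.

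The stopping probabilities are what a reader uses to judge whether the rule is reasonable. One boundary cannot have two stopping probabilities at the same true rate.

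**Working it through.** **1. Cut-offs side by side** (halt when infections exceed the value shown)

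| Patients k | Table | Sentence | Counts where only the sentence halts |
|---|---|---|---|
| 6 | 4 | 4 | none |
| 9 | 6 | 5 | 6 |
| 20 | 11 | 10 | 11 |
| 31 | 16 | 14 | 15, 16 |
| 70 | 32 | 29 | 30, 31, 32 |

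The last row matters less, because accrual is complete by then.

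**2. The other two rules in 8.7.** The steroid-refractory restatement ("if more than 3 out of the first 5 patients, 4 out of the first 8 patients, 5 out of the first 10 patients", then 6 of 13 and 24 of 70) equals its table at all five points. So does the non-relapse-mortality restatement ("if more than 1 out of the first 11 patients, 2 out of the first 26 patients, 3 out of the first 45 patients", then 4 of 65 and 5 of 70). The mismatch is confined to infections.

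**3. Method for the stopping probabilities.** Let q_k(x) be the probability that the trial is still open after k patients with x infections, and p the true rate. Start from q_0(0) = 1 and apply

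q_k(x) = (1 − p)·q_{k−1}(x) + p·q_{k−1}(x − 1).

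After each patient from k = 6 to 70, move all mass with x > b_k to the stopped total. For example, at k = 6 and p = 0.45 the mass stopped is 6 × 0.45⁵ × 0.55 + 0.45⁶ = 0.061 + 0.008 = 0.069.

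The method reproduces the plan's figures for the other two rules within about one percentage point:

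- Steroid-refractory GVHD: 0.100, 0.361, 0.548, 0.819, 0.890, 0.939 (printed 0.10, 0.36, 0.54, 0.83, 0.88, 0.94).
- Non-relapse mortality: 0.102, 0.451, 0.683, 0.773, 0.894 (printed 0.10, 0.45, 0.68, 0.77, 0.89).

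**4. Result for infections**

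| True rate | Printed in table | Printed in sentence | Recursion on printed boundary table |
|---|---|---|---|
| 30% | – | 0.10 | 0.030 |
| 33% | – | 0.18 | 0.063 |
| 35% | 0.10 | – | 0.100 |
| 40% | – | 0.57 | 0.275 |
| 41% | 0.31 | – | 0.325 |
| 45% | 0.55 | 0.83 | 0.554 |
| 50% | 0.79 | 0.96 | 0.816 |
| 55% | 0.96 | – | 0.955 |

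The boundary table matches the first printed set within 3 percentage points and does not match the second. The two printed sets differ by 0.83 − 0.55 = 0.28 at 45% and by 0.96 − 0.79 = 0.17 at 50%.

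**5. A different inequality does not explain it.** If the table meant halting at or above b_k, the recursion would give 0.234 at 35% and 0.707 at 45%, which fits neither set. A count of 15/31 would still be in dispute.

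**6. How often it would matter.** The recursion also gives the chance of meeting a disputed count at k = 9, 20 or 31 while the table has not yet stopped the trial. It is 0.034, 0.086, 0.173, 0.273 and 0.348 at true rates of 30, 35, 40, 45 and 50%. Simulation of 400,000 trials per rate agrees to 0.001.

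| Halted by patient 31 | 40% | 45% | 50% |
|---|---|---|---|
| Table, checked after every patient | 0.157 | 0.304 | 0.496 |
| Sentence, its four cut-offs at 6, 9, 20 and 31 only | 0.281 | 0.480 | 0.686 |

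The second row is a lower bound for the sentence's rule, because it uses only the printed points.

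**7. A possible origin (inference only).** Assume one constant binomial tail limit for k = 6 to 70. A 35% reference rate with limit 0.02435 gives all 65 tabulated values. A 30% reference rate with a limit between 0.0253 and 0.0276 gives all five sentence cut-offs, and stopping probabilities close to the second set (0.82–0.83 at 45%; 0.19–0.20 at 33% against the printed 0.18). This suggests that two designs were left in one section. The documents do not say so, and the contradiction does not depend on it.

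**The case against.** The best defence is that only one complete rule is printed. The text defines stopping through the table, the enrolment rule in 8.7 also works through b, and the table reproduces its own probabilities. On that view the sentence is stale text giving five illustrative points, and a careful reader would apply the table. The trial also has an independent monitoring board and a general power to stop early. The primary test and the sample size are untouched.

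The sizes in step 6 can be challenged too. They assume that each outcome is known before the next patient enrols. With infections followed to day 90 and about 4 enrolments a month, roughly 3 × 4 = 12 patients would be pending at any look, and the enrolment rule allows M = 30. Three of the four disputed counts before full accrual lie below 59% observed: 11/20 is 55%, 15/31 is 48% and 16/31 is 52%. Only 6/9 (67%) lies above it.

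The points on size stand: the figures in step 6 are idealised, and the dispute concerns moderate true rates. The precedence argument does not remove the problem. The sentence says the trial will be halted, nothing marks it as illustrative, and a second set of probabilities is attributed to the same boundaries. General oversight does not tell the board which threshold applies.

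**Conclusion.** The concern holds, and section 8.7 is wrong as written for serious infections. The contradiction in cut-offs (four of five points) and in stopping probabilities (0.55 against 0.83 at 45%, 0.79 against 0.96 at 50%) is read directly from the text and needs no model. Confidence in it is high.

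The practical size is less certain. With independent outcomes known at once, a disputed count arises by patient 31 in about 3% of trials at a true rate of 30%, rising to 35% at 50%. Delayed follow-up and the enrolment rule are not modelled.

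At 59% the printed table stops with probability 0.990, and a rule with lower cut-offs would stop at least as often. What is unsettled is how often the trial would halt at true rates of about 30 to 50%.

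**What to change.** Reconcile the passages to a single infection boundary. From it, derive the restating sentence and one set of stopping probabilities at one list of true rates, and delete the other set. No view is taken here on which version is right. The cost is one re-run of the boundary function and text edits in 8.7, with no extra patients.

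Two minor, separate edits could be made at the same time and carry none of the weight of this point:

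- Complete the unfinished sentence in 8.7 that defines a steroid-refractory event, so that it agrees with 2.3 and 7.1.3.
- Give one historical steroid-refractory rate: 11.2 has 33%, while 8.7 and the synopsis have 38%. This mismatch does not move the printed boundary.
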